10.6.4 Number of Subjects

The investigation population will be comprised of 15-30 SUD patients between 18 to 65 years eligible for study participation according to the inclusion and exclusion criteria. If a subject is a screening failure, it will be replaced with another subject.

10.6.5 Methods of Assigning Subjects to Different Treatment Arms

This investigation will contain up to 30 eligible subjects and there will only be one treatment arm.

10.6.6 Subject Withdrawal, Discontinuation, or Lost to Follow-up

Subjects are free to discontinue participation in the clinical investigation at any time and are not required to give a reason for their decision. However, subjects who discontinue the investigation should, if possible, be asked about the reason(s) for their discontinuation and about the presence of any AE/ADE and, if possible,

	Clinical Investigation Code: KC09-108 Clinical Investigation Plan KCclin02	Revision: A
---	---	----------------

be assessed by an investigator. Discontinuation from the clinical investigation will not affect the future treatment/care of the subject.

If the subject will withdraw his/her consent no further data will thereafter be recorded. Data collected up to the date of withdrawal of informed consent will be used in the data analysis and for the Clinical investigation Report (CIR).

Subjects may be withdrawn from the clinical investigation and assessments at any time, if deemed necessary by the PI.

Specific reasons for withdrawal of subjects from this clinical investigation are:

- The decision of a subject to withdraw from the investigation (including if the subject withdraws informed consent);
- The Principal Investigator deems the subject unfit for the investigation or suspects poor CIP compliance;
- Subject lost to follow-up;

Incorrectly enrolled subjects will be withdrawn from further investigation and assessments. A subject may, however, continue the clinical investigation under exceptional circumstances (i.e. if continuation of investigation or follow-up are necessary for the subject's safety and wellbeing, or if only a follow-up period remain, and the continuation of the investigation is not expected to be associated with any risk or discomfort for the subject).

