10.8.1.3 Follow-up visit (maximum three (3) visits)

Follow-up visits are voluntary and the number of follow-up visits per study subject will be based on the study timeline. There is no specific number of follow-up visits, or time between, that need to be followed.

At Visit 2, 3 and 4 the following assessments will be performed:

- Registration of relevant medication
- Urine pregnancy test for fertile females
- Breath test for measuring drug content with LC/MS-MS analysis
- Time line follow-back on drugs and medicines the last 24 hours information
- Demonstration of PreVict Drugs
- Measurement with PreVict drugs
- Investigator/designee observation during measurement and reply to usability questions
- Questions to study subject
- Questions to PI/designee on PreVict Drugs

	Clinical Investigation Code: KC09-108 Clinical Investigation Plan KCclin02	Revision: A
---	---	----------------

- Recording of adverse events or device deficiencies
- Investigator/designee to inform subject about follow-up visit(s) and /or termination

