10.8.6 Potential Confounding Factors

This is an explorative and early feasibility investigation aiming to collect data on Previct Drugs when it comes to usage and safety.

The collected data is required for further development of Previct Drugs before CE-marking. Future studies will focus on confirming the possibility of drug detection once the development of Previct Drugs is complete and the design has been frozen.

As this is the second pilot investigation using self-administered testing of eyes with a smartphone camera, we do not know how well the subjects can perform a measurement. This is an important usability question and may hamper the aim to collect information if eye measurements can be used for future detection of drug use.

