12 STATISTICAL CONSIDERATIONS

12.1 Statistical Design, Method and Analytical Procedures

All analyses will be performed on the Full Analyses Set (FAS). Full Analyses Set is defined as all subjects included in the clinical investigation with at least one pupillometric measurement. Two light conditions will also be analyzed separately.

Primary analyses: The analysis of the 18 usability questions given in section 10.2 Primary endpoint at visit 1 in the following way:

1. Frequency table for each of the 18 questions with numbers and percentage for each alternative.
2. For answers “very easy” and “easy” and answers, “very good” and “good” favoring Kontigo product will be added together and given with numbers, percentages and 95% confidence intervals.

First secondary analyses: Fraction of collected pupillometry data using native pupillogram. For each of the measurements PLR, NC, and NY the measurements QC control will approve the measurements or not using the native pupillogram. For each subject, the proportion of approved measurements over all measurements during visit 1 will be calculated for each of PLR, NC, and NY. The two light conditions will be analyzed separately. The follow-up analyses will be analyzed separately.

Second secondary analyses: Fraction of collected pupillometry data using refined pupillogram. For each of the measurements PLR, NC, and NY the measurements QC control will approve the measurements or not using the refined pupillogram. For each subject, the proportion of approved measurements over all measurements during visit 1 will be calculated for each of PLR, NC, and NY. The distribution over subjects in each drug class will be given with Mean, SD, median, minimum and maximum. The two light conditions will be analyzed separately. The follow-up analyses will be analyzed separately.

Analysis of demographics and baseline variables: Age, gender, relevant medical and surgical history and the six questions regarding “Timeline follow-back drugs and medicines last 24 hours will be tabulated in a baseline table for FAS population.

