4.7 Handling of Drop-outs, Missing Data and Outliers

Available data from prematurely withdrawn subjects will be included in the analysis as far as possible. Missing data will not be imputed.

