6.4 Compliance of Investigational Medical Device (IMD)

During each measurement the PreVict Drugs app will inform if the conducted test was approved. If not approved, the subject will be asked to re-do the measurement. If the test cannot be conducted, the subject continues to the next test, or completes the test set, as applicable.

Performed and successful tests are documented in the eCRF for Visit 1 and if applicable for the follow-up visits. The number of attempts per test is not documented in the eCRF. During the on-site visits, compliance is overseen by site personnel. Sponsor is the only part receiving the PreVict Drugs data output. Non-compliance related to PreVict drugs measurements will be documented by the Sponsor, and where applicable be reported as Protocol Deviations.

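### Withdrawal for suspected poor compliance is not separated from difficulty in using the device, so weak users could drop out of the follow-up results, which are compared with visit 1 without pairing

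*Protocol*

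**What the plan says.** Protocol 10.6.6 gives the investigator general discretion: "Subjects may be withdrawn from the clinical investigation and assessments at any time, if deemed necessary by the PI". Among the specific reasons it lists: "The Principal Investigator deems the subject unfit for the investigation or suspects poor CIP compliance". Suspicion is enough, and poor compliance is not defined.

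SAP 6.4, which deals with device compliance, first says that an unapproved measurement is repeated, and then: "If the test cannot be conducted, the subject continues to the next test, or completes the test set, as applicable". It adds that site personnel oversee compliance at the visits, and that "Non-compliance related to PreVict drugs measurements will be documented by the Sponsor, and where applicable be reported as Protocol Deviations". Non-compliance is not defined there either.

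On the purpose of the study, Protocol 10.8.6 says "we do not know how well the subjects can perform a measurement. This is an important usability question". Follow-up visits are voluntary and include "Investigator/designee observation during measurement and reply to usability questions" (Protocol 10.8.1.3).

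On analysis, Protocol 12.1 places the primary analysis at the first visit: "The analysis of the 18 usability questions given in section 10.2 Primary endpoint at visit 1 in the following way". SAP 7 presents efficacy results by visit. SAP 7.2.2 analyses follow-up separately and compares it with the visit 1 success rate. For withdrawn subjects, SAP 4.7 says: "Available data from prematurely withdrawn subjects will be included in the analysis as far as possible. Missing data will not be imputed".

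**The concern.** In most trials, poor compliance and poor outcome are different things. Here they overlap. The subject's main task is to follow the app's instructions and complete the measurements, and the study asks how well people with substance use disorder can do so. A subject who gives up or does not follow the prompts gets an unfavourable usability rating and may also look like someone with poor compliance.

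If such subjects are withdrawn after visit 1, they remain in the visit 1 figures and are missing from the follow-up figures. The follow-up rates then rise even if nobody has improved, and the planned comparison with visit 1 could be read as a learning effect. The study would also lose its chance to see whether weak users improve with repetition, although Protocol 10.6.7 says that data from several visits would be valuable for usability.

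**Working it through.** The plan has no figure to reproduce: it states no withdrawal rate, no expected success rate and no sample size calculation.

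**Step 1: does the text allow it?** Protocol 10.6.6 needs only suspicion and does not separate unwillingness from inability. SAP 6.4 discusses unapproved, repeated and non-conductible tests alongside an undefined non-compliance. Neither section links a failed test to withdrawal, and neither rules the link out. The route is therefore permitted but not prescribed.

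**Step 2: which results can move?**
- Visit 1 usability (primary) and visit 1 proportions (secondary): a withdrawal after visit 1 leaves them unchanged. Collected data are kept (Protocol 12.10, SAP 4.7), and the full analysis set has no compliance exclusion (SAP 4.2.2). One gap remains: a subject withdrawn before any pupillometric measurement falls outside that set.
- Follow-up usability and success rates: these rest on whoever is still in the study and returns, so they can move.

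**Step 3: by how much?** All inputs here are assumptions. Let *f* be the share of weak users at visit 1, *pg* and *pb* the success rates of good and weak users, and *w* the share of weak users withdrawn after visit 1. Each subject's rate stays constant, and everyone not withdrawn returns.

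- Visit 1 rate = (1 − f)·pg + f·pb
- Follow-up rate = [(1 − f)·pg + f(1 − w)·pb] / [(1 − f) + f(1 − w)]

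Example with f = 0.2, pg = 0.9, pb = 0.3, w = 0.5: visit 1 = 0.8 × 0.9 + 0.2 × 0.3 = 0.78; follow-up = (0.72 + 0.03) / (0.8 + 0.1) = 0.833; shift +5.3 points.

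| f | pb | Visit 1 | Follow-up, half withdrawn | Follow-up, all withdrawn | Shift (points) |
|---|---|---|---|---|---|
| 0.2 | 0.3 | 0.78 | 0.833 | 0.90 | +5.3 to +12 |
| 0.2 | 0.6 | 0.84 | 0.867 | 0.90 | +2.7 to +6 |
| 0.4 | 0.3 | 0.66 | 0.75 | 0.90 | +9 to +24 |
| 0.4 | 0.6 | 0.78 | 0.825 | 0.90 | +4.5 to +12 |

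(pg = 0.9 throughout.) The formula uses shares only, so the result is the same for 15 or 30 subjects.

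**Step 4: effect of pairing.** In subjects with both visits, the change is 0 in every row, because each subject's rate is held constant. Pairing removes the false gain. It does not supply the follow-up visits of weak users who were withdrawn.

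**The case against.** The strongest reply is that nothing in the documents turns a failed measurement into a withdrawal. SAP 6.4 tells the subject to carry on. The sponsor, not the investigator, documents measurement non-compliance and alone receives the device output. The usability questions already record difficulty, need for support and number of efforts, so withdrawing someone for clumsiness would go against the design. Withdrawals would also be visible: SAP 5.1 counts them and the numbers at each visit, and SAP 9 lists discontinued patients and deviations.

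Most of this stands. A reader might infer that the SAP classes measurement problems as non-compliance and that the main usability result is therefore inflated. The documents support neither step: the SAP leaves the term undefined, and the primary and main secondary results are at visit 1.

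Two things remain. Site staff oversee compliance and the investigator or designee rates usability, so the site does see who performs poorly when withdrawal is considered. And SAP 5.1 counts withdrawals without specifying a summary by reason, so a selective pattern would not be obvious from the tables.

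A further fair objection is that follow-up is voluntary. Weak users who simply do not return cause the same shift without any action by the investigator. This does not remove the point, but it means that changing the withdrawal wording alone is not enough.

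**Conclusion.** The concern holds in a limited form. The withdrawal wording permits removal that depends on the outcome, and the follow-up comparison is not protected against it. The effect falls on follow-up; visit 1 results are largely safe.

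The range of about +3 to +24 points rests on assumed shares of weak users (20% or 40%), assumed success rates (0.9 against 0.3 or 0.6), withdrawal of half or all weak users, and no true change over time. It shows what could happen and is not a forecast; if no weak user is withdrawn and all return, the shift is zero. For a descriptive pilot with no hypothesis and no pass or fail criterion, the point is minor to moderate.

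**What to change.** 1. **Protocol 10.6.6.** Restrict the suspected-compliance ground to conduct unrelated to device performance, and add: *Failure or difficulty in performing or completing a Previct Drugs measurement is a study outcome and is not in itself a ground for withdrawal.* The investigator's discretion over unfit subjects stays unchanged.
2. **SAP 6.4.** Define non-compliance to match, and count such cases as not approved or not performed in the analysis. Continue to list them as deviations where Protocol 15 requires it. That section covers unintentional as well as deliberate departures, so taking these cases out of deviation reporting would contradict it; an event can be both an outcome and a deviation.
3. **SAP 7.2.2.** Compare follow-up with visit 1 in subjects who have both visits. This also deals with the false gain from voluntary non-return.
4. **SAP 5.1.** Tabulate the reason for each withdrawal by the investigator.

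The cost is a few sentences in the two documents and one small table. The downside is that follow-up figures may look slightly less favourable, because more failed measurements will be seen and counted.

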10.6.7 Subject Follow-up and Care

Each subject will participate for a minimum of 1 day and a maximum of four (4) weeks after the baseline visit. This investigation period has been decided to be appropriate as it will provide usability data in a population Previact Drugs is intended for. The flexible follow-up period has been decided based on that it is difficult to schedule follow-up visits for this population and that data collection from one visit is enough even though that it would be valuable from a usability perspective to collect data from several visits.

If the clinical investigation is prematurely terminated, the sponsor and the PI(s) will assure that adequate consideration is given to the protection of subjects' interest, including subject follow-up.

10.7 Clinical Investigation Duration

Point of enrolment:	Q1 2023
Point of randomization:	Not applicable
Enrolment period:	4 months
Expected duration of each subject's participation:	1 month
Total expected duration of the clinical investigation:	5 months

10.8 Clinical Investigation Procedures

10.8.1 Schedule of Clinical Investigation Procedures /Assessments

The assessments and procedures that will be performed during the clinical investigation is illustrated in Table 3 below. Further information is provided in the sections below.

Table 3. Clinical Investigation schedule for assessments and procedures.

Assessment	Before visit 1	Visit 1 Day 0	Follow-up visit(s)	Termination
Study information (written and oral)	X			
Signing Informed Consent		X		
Inclusion/Exclusion criteria		X		
Pregnancy test for fertile women (urine)		X	X	

	Clinical Investigation Code: KC09-108 Clinical Investigation Plan KCclin02	Revision: A
---	---	----------------

Assessment	Before visit 1	Visit 1 Day 0	Follow-up visit(s)	Termination
ECG (if older than 2 years)		X		
Relevant concomitant medication		X		
Medical and surgical history		X		
Breath test (sample collection for LC/MS-MS analysis)		X	X	
Subjects Demographics ¹		X		
Timeline follow-back drugs and medicines last 24 hours		X	X	
Demonstration of Previct Drugs		X	X	
Measurements with Previct Drugs		X	X	
PI/designee questionnaire /observation (usability)		X	X	
Questions to PI/designee on Previct Drugs		X	X	
Adverse event and/or device deficiency		X	X	X
PI/designee inform subject about follow-up visits(s) ²		X	X	
End of investigation				X

Notes:

¹Age, gender

²Maximum four (4) follow-up visits, incl visit 1.

10.8.1.1 Subject information (Before visit 1)

Prior to the baseline and visit at Day 0, potential subjects that are interested to participate will contact the site. A poster at the investigational site will inform about the study. The site personnel will give information about the study and perform a brief check towards the eligibility criteria. The investigator or designee will introduce the clinical investigation and explain the objectives of the investigation and assessments and procedures to be performed to a potential subject. The investigator will verbally inform the patient about the study in an understandable manner. The oral information will be an important part before the consenting process. It will be given at the study site, and then the patient can ask questions and return at later occasion before consenting and enrolment in the study. Any queries that a potential subject may have regarding the investigation will be addressed appropriately by the investigator. Potential subjects will be instructed that they are free to obtain further information from the investigator at any time and that they are free to withdraw their consent and to discontinue their participation in the investigation at any time without prejudice.

10.8.1.2 Visit 1 (Baseline Visit)

Before any investigation-related procedures are initiated, the informed consent form (ICF) must be signed and dated by the subject and by the investigator who gave the subject the verbal and written information. The original ICF document will be retained in the Investigator Site File (ISF) and a copy provided to the subject. The investigator must obtain written informed consent from the subject before any clinical investigation-related procedures are performed, for further details on the informed consent process please see section 18.

After written informed consent has been obtained the subject is considered as enrolled. The subject will be allocated to the next available subject ID number, used for the identification of the subject in the investigation.

An enrolled subject will go through the screening parameters, e.g., relevant medical/surgical history, review of relevant current medication, and information on the subjects' demographics. ECG examination will be performed if the existing measurement is older than 2 years. The investigation also requires that a pregnancy test in fertile female subjects is analyzed. A breath test ~~urine~~ test will be performed for determine the drug

	Clinical Investigation Code: KC09-108 Clinical Investigation Plan KCclin02	Revision: A
---	---	----------------

content through LC/MS-MS analysis. Information on a subject's drug intake will be collected in the timeline follow-back of drugs and medicines last 24 hours.

After confirmation of the inclusion and exclusion criteria, the subject will be assessed as eligible. If the subject is not eligible, i.e., not fulfilling one of the inclusion criteria or fulfilling one of the exclusion criteria, the subject is to be seen as a screening failure and should be terminated from continuing in the investigation.

Previct Drugs measurement

The first test with PreVict Drugs will take place once the subject has been assessed as eligible. The site personnel will demonstrate for the subject how PreVict Drugs shall be used according to the IFU, and the procedures described in this CIP. The site personnel will assist as required during a test with PreVict Drugs. The subject will perform an eye measurement series which consists of four performed measurements:

- 1 Cross-eyes test
- 1 Nystagmus test
- 2 Contraction tests

The contraction tests must be performed under two different light conditions. The subject must begin by performing a cross-eye-test, followed by a nystagmus test, and then a contraction test. Adjust the lighting conditions, wait 1 minute, and then perform the second contraction test.

At Visit 1, the following assessments/procedures will be performed:

- Informed consent
- Demographics:
 - Age
 - Gender
- Registration of relevant medication
- Relevant medical and surgical history
- ECG (if existing < 2 years)
- Urine pregnancy test for fertile females
- Breath test for measuring drug content with LC/MS-MS analysis
- Time line follow-back on drugs and medicines the last 24 hours information
- Demonstration of PreVict Drugs
- First test with PreVict drugs
- Investigator/designee observation during measurement and reply on usability questions
- Questions to study subject
- Questions to PI/designee on PreVict Drugs
- Recording of adverse events or device deficiencies
- Investigator/designee to inform subject about follow-up visit(s) and /or termination

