This study population was selected to obtain data on usability for a similar population for which the product will be used in the future, as well as to collect eye data on patients with a current addiction.

Applicable inclusion and exclusion criteria have been decided based on the subject population to have a homogenic group, minimize aspects that may interfere with the results of the study, and making sure that any potential risks and safety concerns have been addressed during the screening period before confirming a subject is eligible for participation.

	Clinical Investigation Code: KC09-108 Clinical Investigation Plan KCclin02	Revision: A
---	---	----------------

8 BENEFITS AND RISKS OF THE INVESTIGATIONAL DEVICE, CLINICAL PROCEDURE, AND CLINICAL INVESTIGATION

When discussing benefits and risks of a new medical device, there are different aspects that have to be considered, including the potential benefits and risks for the subjects participating in the clinical investigation and for future patients with clinical use of the new device.

The risk management related to PreVict Drugs has been conducted in accordance with ISO 14971:2020 and included risk analysis, risk evaluation, and risk control.

The below will summarize potential risks and benefits related to the product, PreVict Drugs, and the ones for the clinical investigation related to the study design, assessments, and study population. For detailed information on the performed risks analyses, see respective report/analysis [18-19].

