10.6.2 Exclusion Criteria

Subjects meeting any of the following criteria will not be permitted to participate in the investigation:

1. Participating in another clinical investigation which may affect the study outcome according to clinical judgement
2. Pregnancy or lactating
3. Blind
4. Deaf
5. Any ECG dangerous arrhythmia according to the investigator or designee judgment
6. Any disease or condition that may influence pupillary reflexes based on clinical judgement
7. Undergone eye surgery that may influence pupillary reflexes based on clinical judgement
8. Not able to read or understand the local language
9. Any planned travel or treatment which will make it impossible to participate according to the investigator or designee
10. Any other condition that as judged by the investigator may make the follow-up or investigation appropriate
11. That according to the Declaration of Helsinki is deemed unsuitable for study enrolment

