10.8.2 Screening/Baseline Measurements

The data collected at visit 1 during screening and baseline will describe the study population and confirm eligibility. Age and gender will be recorded. ECG, if older than 2 years, relevant medical and surgical history and relevant current medication will be recorded. Relevant medical and surgical history is defined as any previous or existing condition that may potentially affect the outcome of the study according to the best judgment of the investigator or designee.

Pregnancy test and confirmation

Woman of childbearing potential (defined as all women who are not surgically sterile or postmenopausal for at least 1 year prior to enrollment) must have a negative urine pregnancy test at enrollment. If the pregnancy test is positive the subject is not eligible and cannot be enrolled in the investigation.

Exhaled breath test drug testing (Breath Explorer®)

To measure the actual content of drugs a breath test will be performed. The breath test is not mandatory and will be carried out on a voluntary basis. This test will be used for a qualitative detection of thirty-six (36) most common drugs using LC-MS/MS analysis method.

3_CMC, 4-flouro amphetamine, 4-FMA, 4-MMC, 6-MAM, alprazolam, amphetamine, buprenorphine, BZE, CBD, clonazepam, codeine, diazepam, EDDP, ephedrine, flunitrazepam, gabapentinin, hydromorphone, ketamine, cocaine, lorazepam, LSD, MDMA, methadone, methylamphetamine, methylfenidat, morphine, oxazepam, oycodone, pentedrone, pregabalin, temazepam, THC, tramadol zolpidem, zopiclone.

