12.2 Sample size

The investigation aims to enroll up to 30 SUD subjects.

As this is an early feasibility and explorative investigation, the sample size is not derived from a sample size calculation as no hypothesis is pre-defined. It is based on available subjects from the clinic.

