5.2 Baseline Characteristics and Demographics

Demographics (e.g., age, gender,) and baseline characteristics (e.g., ECG, relevant medical and surgical history, relevant concomitant medication, timeline follow-back drugs and medicine last 24-hours) will be presented using descriptive statistics.

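### The visit 1 procedure list reverses the ECG condition given in three other places in the protocol, and no version covers a subject with no earlier ECG

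*Protocol*

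**What the plan says.** The protocol states the condition for the ECG in four places.

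- Section 10.8.1, Table 3, has a row marked at visit 1 only: "ECG (if older than 2 years".
- The narrative of section 10.8.1.2 (Visit 1) has the one full sentence on the matter: "ECG examination will be performed if the existing measurement is older than 2 years".
- The bulleted list later in section 10.8.1.2, which sets out what is to be done at visit 1, has "ECG (if existing < 2 years".
- Section 10.8.2 (Screening/Baseline Measurements) has "ECG, if older than 2 years, relevant medical and surgical history and relevant current medication will be recorded".

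The ECG bears on eligibility through exclusion criterion 5 in section 10.6.2, repeated in the synopsis: "Any ECG dangerous arrhythmia according to the investigator or designee judgment". Under section 10.8.1.2, eligibility is confirmed at visit 1, before the first test with the device. Section 7 gives one purpose of the criteria as "making sure that any potential risks and safety concerns have been addressed during the screening period before confirming a subject is eligible for participation".

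SAP section 5.2 counts the ECG among the "baseline characteristics (e.g., ECG, relevant medical and surgical history" and other items to be summarised, and SAP section 9 includes ECG among the data listings. Neither attaches a condition on the age of the tracing.

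**The concern.** The threshold is 2 years in all four places, but the direction changes in one of them. That one is the bulleted list, which site staff would naturally use as their checklist for the visit. It also sits in the same section as the full sentence that it reverses.

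What is at stake is which subjects have a new tracing when criterion 5 is judged. If the list is followed as written, the subjects with the oldest tracings get no new one, and those with recent tracings get a second. Section 15 forbids departures from the protocol and prohibits waivers, yet a site that follows either wording departs from the other.

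A second gap lies beside the first. All four statements turn on the age of an ECG that already exists. None says what is to happen when there is none.

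**Working it through.** No calculation in the plan bears on this point, and there is no planned figure to reproduce: section 12.2 says that "the sample size is not derived from a sample size calculation as no hypothesis is pre-defined". The check is a comparison of the four statements.

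**Step 1. Direction of each statement**

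| Place in the protocol | Condition for the ECG |
|---|---|
| 10.8.1, Table 3 | existing ECG older than 2 years |
| 10.8.1.2, narrative | existing ECG older than 2 years |
| 10.8.1.2, procedure list | existing ECG less than 2 years old |
| 10.8.2 | existing ECG older than 2 years |

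Three statements run one way and one runs the other.

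**Step 2. What each wording implies for a given subject**

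Let *a* be the age in years of the subject's existing ECG. The list calls for an ECG when *a* < 2. The other three call for one when *a* > 2.

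| Subject's existing ECG | ECG at visit 1 under the list? | ECG at visit 1 under the other three? | Same answer? |
|---|---|---|---|
| less than 2 years old | yes | no | no |
| exactly 2 years old | no | no | yes |
| more than 2 years old | no | yes | no |
| none | not addressed | not addressed | neither gives a rule |

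The first and third rows are the contradiction. The fourth row is the separate gap, and it is the same under every wording.

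**Step 3. Consequence for criterion 5**

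- Third row, list followed: the criterion is judged on a tracing more than 2 years old. The subject has an ECG, but not the new one that the other three statements call for.
- First row, list followed: the subject has an additional ECG that the other three statements do not call for.
- Fourth row, any wording: the criterion could be judged with no tracing at all.

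**Step 4. How many subjects**

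Sections 10.6.4 and 12.2 put the maximum at 30 subjects. Write *n* = *r* + *e* + *o* + *z* for those whose ECG is recent (*a* < 2), exactly 2 years old, old (*a* > 2) or absent. The wordings disagree for *r* + *o* subjects, criterion 5 could rest on an old tracing for *o*, and it could rest on no tracing for *z*. The documents give none of these counts. Without an outside assumption, each can lie anywhere from 0 to 30, subject to the total.

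**Step 5. What else in the plan uses the ECG**

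The primary endpoint is the 18 usability questions. The secondary endpoints are fractions of pupillometry data that pass quality control. Neither uses the ECG. The baseline table in protocol section 12.1 does not name it either. Its only statistical uses are the descriptive summary in SAP section 5.2 and the listing in SAP section 9. If those hold tracings made at visit 1, the two wordings fill them from complementary groups of subjects.

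**The case against.** The strongest reply is that the list entry is shorthand. The only complete statement of the rule stands shortly before it in the same section, and Table 3 and section 10.8.2 agree with that statement. The list also mixes record review, such as medical history and medication, with procedures. The entry might therefore mean that an existing ECG less than 2 years old is to be used, which would fit the narrative. The entry in section 10.8.2 is elliptical as well: taken word for word, it has an ECG recorded if it is old. On this view the plan has one rule and one badly worded bullet, and a careful site would work out the intent.

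That reading is possible, but the text does not state it. The entry appears among things to be carried out at visit 1, and nothing there says that it refers to accepting a tracing already on file. Agreement among three of four statements shows where the conflict lies without removing it from the list that a site would use.

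Other parts of the reply do stand. Criterion 5 rests on the judgement of the investigator or designee and sets no date for the ECG. The protocol does not itself call it a safety exclusion; that reading comes from its wording and from section 7. The protocol describes the risk from using the device as low or non-existing (sections 8.2 and 8.5). The SAP does not limit its ECG summary to tracings made at visit 1.

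A reader might also infer two stronger things. The first is that all subjects are classified oppositely. This fails for anyone with no earlier ECG, and for an ECG exactly 2 years old. The second is that the reversed wording lets criterion 5 be applied without an ECG. It does not: a subject with an old tracing still has that tracing. Only a subject with no ECG on file could be judged without one, and that follows from the gap common to all four statements.

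**Conclusion.** The contradiction is real and stands in the current text. Read literally, the list and the other three statements disagree for every subject with an existing ECG, apart from one exactly 2 years old. The practical consequence is that criterion 5 could be judged on a tracing more than 2 years old in subjects for whom three of the four statements call for a new one. The gap for subjects with no earlier ECG is a separate defect. Correcting the direction of one bullet would not close it.

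The reach is limited to the eligibility decision and the baseline ECG data. The sample size and the primary and secondary analyses do not change. The conclusion rests on reading the list entry literally as a condition for performing an ECG. The effect on the SAP's ECG data rests on the further assumption that they include tracings made at visit 1. The number of subjects concerned cannot be derived from the documents. No view is taken here on which condition is clinically right.

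**What to change.** The sponsor and investigator should choose one ECG condition and state it identically in Table 3, in the narrative and the procedure list of section 10.8.1.2, and in section 10.8.2. The condition should also say what applies to a subject with no earlier ECG. It would help if SAP section 5.2 stated whether the ECG summary covers tracings made at visit 1, tracings already on file, or both. The main change costs protocol wording only, handled under the amendment procedure in section 14; the SAP clarification is a single sentence. No analysis has to be redesigned.
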